4.6.1.2 DAS28-CRP and DAS28-ESR scores

The change from baseline in DAS28-CRP and DAS28-ESR at all visits will be analyzed using the same MMRM method as for primary endpoint analysis (see Section 2.4.1).

DAS28-CRP and DAS28-ESR at baseline and weeks 2, 4, 12, 24, 36 and 48, and DAS28-CRP and DAS28-ESR change from baseline at weeks 2, 4, 12, 24, 36 and 48, will be summarized by treatment and visit using descriptive statistics. For DAS28-CRP and DAS28-ESR, the spaghetti plots by treatment and site will be provided, individual patient profile will also be provided.

4.6.1.3 Analysis of EULAR over time

The number and proportion of patients achieving EULAR good and moderate response, as well as EULAR remission criteria in DAS28-ESR at weeks 2, 4, 12, 24, 36 and 48 will be summarized and plotted by treatment and visit.

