#### **6.4.1 Assessment of Disease Activity Score (DAS28)**

The disease activity score (DAS) is a combined index to measure the disease activity in patients with RA. In this study DAS28-CRP and DAS28-ESR will be measured. The DAS28-CRP will be used for primary and key secondary endpoint analysis, whereas DAS28-ESR will only be used for secondary endpoint analysis. The efficacy assessments will be done at screening, baseline, Week 2, Week 4, Week 12, Week 24 and Week 48 (Visits 1, 2, 3, 4, 8, 14 and 16).

In order to calculate the DAS28-CRP or DAS28-ESR, information about the following disease variables is needed:

The number of swollen joints and tender joints should be assessed using 28-joint count (TJC28 and SJC28), see [Figure 6-1](#).

The patient's general health (GH) or global disease activity measured on a Visual Analogue Scale (VAS) of 100 mm (both are useable for this purpose) must be obtained ([Prevoo et al 1995](#)).

CRP should be measured in mg/L

and

ESR should be measured in mm/hour.

Using this data, the DAS28 can be calculated using the following formula:

**DAS28-CRP** = 0.56 \* sqrt(TJC28) + 0.28\* sqrt(SJC28) + 0.36 \* ln(CRP+1) + 0.014 \* GH + 0.96

**DAS28-ESR** = 0.56 \* sqrt(TJC28) + 0.28 \* sqrt(SJC28) + 0.70 \* ln(ESR) + 0.014 \* GH

Swollen joints, tender joints and patient's general health assessment will be entered into the eCRF and CRP/ESR will be used to determine DAS28-CRP and DAS28-ESR scores.

In addition CRP values provided by the central laboratory at both screening and Week 22 will be entered into the eCRF and be used to calculate DAS28-CRP scores for the purpose of assessing eligibility at randomization and Week 24 only (see [Table 6-1](#)).

The DAS28 provides a number on a scale from 0 to 10 indicating the current activity of the RA of the patient. Disease activity definition is described in [Table 6-2](#).

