### **9.5.2 Efficacy**

Efficacy variables will be presented for both the FAS and PPS analyses sets and include:

- DAS28-CRP, DAS28-ESR
- ACR20, ACR50, ACR70 (CRP & ESR) response rate
- CRP, ESR
- HAQ-DI
- FACIT Fatigue scale.

Incidence rates over time shall be presented for ACR 20/50/70 and DAS28-CRP EULAR defined criteria. Summary statistics of absolute and change from baseline for DAS28-CRP & ESR and CRP & ESR values will be provided.

For Treatment period 2 summary statistics of DAS28-CRP & ESR scores changes from Week 24 at Week 48 will be presented, in addition to incidence rates for ACR 20/50/70 at Week 48.

The quality of life assessments HAQ-DI and FACIT Fatigue Scale will be summarized for absolute values and change from baseline at Week 4, 12 and 24 and for change from Week 24 at Week 48. In addition incidence rates of patients achieving a HAQ-DI score of  $\leq 0.5$  and a score improvement of  $> 0.3$  shall be presented.

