2.1.2 General considerations

Raw data listings, summary tables, figures and statistical tests will be generated using the SAS® Version 9.4 or higher.

All clinical data, including laboratory, immunogenicity, and pharmacokinetics data will be provided as raw data from an external database. CDISC SDTM 3.1.2 amendment 1 compliant SAS® datasets will be prepared. The final SDTM files will also include variables indicating the actual and planned treatment assigned.

Coding of corresponding data (e.g. by Medical Dictionary for Regulatory Activities [MedDRA] or World Health Organization [WHO]-drug dictionary), and ATC coding is included in the SDTM datasets.

Appropriate SAS® programs will be prepared and validated according to standard operating procedures.

The following descriptive statistics will be shown in summary tables:

- Continuous variables: n (number of patients with evaluable data), mean, standard deviation (SD), minimum, median, maximum. Quartiles will be presented as appropriate.
- Categorical variables: Count and percentage of each category. A row denoted “Missing” will be included in count tabulations where necessary to account for dropouts and missing values. Unless otherwise specified, the denominator for all percentages will be the number of patients in the treatment group within the analysis set of interest. Percentages will not be provided if the number is zero.

The same number of decimal places as in the raw data will be presented when reporting minimum and maximum, 1 more decimal place than in the raw data will be presented when reporting mean, median and quartiles, and 2 more decimal places than in the raw data will be presented when reporting SD and SE.

For the derived variables, appropriate precision should be provided in CSR appendix data listing. E.g., for the DAS28-CRP and DAS28-ESR, 2 decimal places will be kept in the data listing, the decimal places of the descriptive statistics will then follow the rules above accordingly (i.e., treat raw data as 2 decimal places).

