2.2 Study objectives and endpoints

The study objectives and related endpoints see [Table 2-1](#).

Table 2-1 Objectives and related endpoints

Objectives	Endpoints
Primary objectives 
• To demonstrate similar efficacy of GP2017 and US-licensed Humira® in patients with moderate to severe active RA up to Week 12	Primary endpoint 
• DAS28-CRP score change from baseline up to Week 12
Key secondary objective 
• To demonstrate similar efficacy of GP2017 and US-licensed Humira® in patients with moderate to severe active RA until Week 24	Key secondary endpoint 
• Time-weighted averaged change from baseline in DAS28-CRP until Week 24
Other secondary objectives in Study Period 1 
• To demonstrate similar efficacy and to compare safety and immunogenicity of GP2017 and US-licensed Humira® in patients with moderate to severe active RA over 24 weeks of treatment	Other secondary endpoints in Study Period 1 
• Proportion of GP2017 and US-licensed Humira® treated patients achieving EULAR criterion for remission at Week 4, 12, 24• Proportion of GP2017 and US-licensed Humira® treated patients achieving EULAR criterion for good response at Week 4, 12, 24• Proportion of GP2017 and US-licensed Humira® treated patients achieved EULAR moderate response at Week 4, 12, 24• DAS28-CRP and DAS28-ESR changes from baseline in GP2017 and US-licensed Humira® treated patients at Week 2, 4, 24

Objectives	Endpoints

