2.3.1.4 EULAR response criteria

The EULAR good response, moderate response, and no response based on the DAS28-CRP are defined as follows.

Table 2-2 EULAR response criteria

Improvement in DAS28 from baseline			
Present DAS28	> 1.2	> 0.6 and ≤ 1.2	≤ 0.6
≤ 3.2	good response	moderate response	no response

Improvement in DAS28 from baseline			
Present DAS28	> 1.2	> 0.6 and \leq 1.2	\leq 0.6
> 3.2 to \leq 5.1	moderate response	moderate response	no response
> 5.1 (high)	moderate response	no response	no response

EULAR remission is defined as DAS28-CRP < 2.6.

If the DAS28-CRP is missing then the EULAR response is set to missing. Note that it is a condition of continuation into SP2 that a patient show at least a moderate response based on DAS28-CRP at Week 24 (using Week 22 CRP values).

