4.2 Disposition of patients and protocol deviations

Frequency and percentage of patient's recruitment by region, country, site, and treatment group will be presented.

Disposition of patients includes the number and percentage of patients for the following categories: randomized, completed Week 12, discontinued before Week 12, completed SP1, discontinued during SP1, eligible to enter SP2 (achieving at least a moderate EULAR response assessed by DAS28-CSR at Week 24), entered SP2, completed SP2, discontinued during SP2. The primary reason for discontinuation in SP1/SP2 will be summarized.

A patient who completed the Visit 14 (Week 24) is considered to have completed SP1.

Frequency and percentage of patients having major and minor protocol deviations will be presented by deviation category, treatment group and overall for all patients in FAS. Patient having major and minor protocol deviations will be counted only once under more severe deviation category. Patients who are excluded from each analysis population and protocol deviations will also be listed.

All percentages for the summaries will be based on the number of patients in FASs (SP1 FAS for study period 1 and during the entire study, or, SP2 FAS for study period 2).

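### SAP 4.6.1.3 summarises EULAR remission on DAS28-ESR, while SAP 2.3.1.4 and protocol 9.5.2 base it on DAS28-CRP

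*SAP*

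**What the plan says.** EULAR remission is a listed secondary endpoint. SAP Table 2-1 asks for the proportion of "treated patients achieving EULAR criterion for remission at Week 4, 12, 24", and the protocol objective in section 2.2 matches it. Neither names CRP or ESR, so the index has to come from elsewhere.

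- **SAP 2.3.1.4 (definition).** For response: "The EULAR good response, moderate response, and no response based on the DAS28-CRP are defined as follows". For remission: "EULAR remission is defined as DAS28-CRP < 2.6". The section also sets EULAR response to missing when DAS28-CRP is missing.
- **Protocol 9.5.2 (planned presentation).** "Incidence rates over time shall be presented for ACR 20/50/70 and DAS28-CRP EULAR defined criteria".
- **SAP section 2.** The data are to be analysed as described in section 9 of the protocol, which contains 9.5.2.
- **SAP section 3 (changes to planned analyses).** No change of index for the EULAR criteria is listed.
- **SAP 4.6.1.3 (analysis section).** "EULAR good and moderate response, as well as EULAR remission criteria in DAS28-ESR" is to be summarised and plotted at Weeks 2, 4, 12, 24, 36 and 48.

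**The concern.** SAP 4.6.1.3 is the section a programmer would follow to build the EULAR tables, and for remission it names a different index from the definition those tables should implement. DAS28-CRP and DAS28-ESR share the joint counts and the patient global assessment. They differ in the inflammation marker, its coefficient and the constant term, so one patient at one visit can be in remission on one score and not on the other. The source data differ as well: CRP is measured centrally and ESR locally (protocol 6.4.9 and 6.4.10), so the two scores need not be missing for the same patients.

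What is at stake is whether a listed secondary endpoint is reported on the index that defines it. Settled in the text, the choice is not left to whoever writes the program. Left open, it could look like a choice made after the data were seen.

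**Working it through.** There is no sample size, power or alpha figure to reproduce here. The check has two parts: compare the texts, then see whether the index can matter for a patient.

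**1. Texts side by side**

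| Place | Remission | Good and moderate response |
|---|---|---|
| SAP 2.3.1.4 | DAS28-CRP, below 2.6 | DAS28-CRP |
| Protocol 9.5.2 | DAS28-CRP | DAS28-CRP |
| SAP 4.6.1.3 | DAS28-ESR | DAS28-ESR, or no index named |

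The phrase naming DAS28-ESR may attach to remission alone or to the whole list. Remission conflicts with the definition under either reading. Good and moderate response conflict only under the second, so nothing below rests on them.

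**2. Can the index change remission status?**

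Formulas (protocol 6.4.1; SAP 2.3.1.2 and 2.3.1.3):

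- DAS28-CRP = 0.56 √TJC28 + 0.28 √SJC28 + 0.36 ln(CRP + 1) + 0.014 PtGA + 0.96
- DAS28-ESR = 0.56 √TJC28 + 0.28 √SJC28 + 0.70 ln(ESR) + 0.014 PtGA

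With the shared terms cancelled, DAS28-ESR minus DAS28-CRP = 0.70 ln(ESR) − 0.36 ln(CRP + 1) − 0.96.

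The documents give no joint distribution of ESR and CRP, so every patient value here is an assumption. Over an assumed range of ESR 5 to 40 mm/h and CRP 1 to 20 mg/L:

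- lowest, at ESR 5 and CRP 20: 1.127 − 1.096 − 0.96 = −0.93
- highest, at ESR 40 and CRP 1: 2.582 − 0.250 − 0.96 = +1.37

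The scores agree when ESR = exp[(0.96 + 0.36 ln(CRP + 1)) / 0.70]. At CRP 5 mg/L this is exp(1.605 / 0.70) = 9.9 mm/h.

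Two illustrative patients, both with PtGA 20 mm and CRP 5 mg/L:

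- **Patient A** (TJC28 1, SJC28 0, ESR 20).
  - CRP: 0.56 + 0 + 0.645 + 0.28 + 0.96 = 2.445, remission.
  - ESR: 0.56 + 0 + 2.097 + 0.28 = 2.937, not remission.
- **Patient B** (TJC28 1, SJC28 1, ESR 5).
  - CRP: 0.56 + 0.28 + 0.645 + 0.28 + 0.96 = 2.725, not remission.
  - ESR: 0.56 + 0.28 + 1.127 + 0.28 = 2.247, remission.

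Status can therefore move in both directions. These are existence examples and say nothing about how often it would happen.

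**3. Week 36**

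SAP 4.6.1.3 lists Week 36. Protocol 6.4.1 schedules the DAS28 assessments at screening, baseline and Weeks 2, 4, 12, 24 and 48. CRP and ESR are drawn at Week 36, but the patient global assessment is not scheduled then (protocol 6.4.5), and SAP 2.3.1.2 and 2.3.1.3 leave the score missing when a component is missing. There is thus no scheduled score to summarise at Week 36 on either index.

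**The case against.** The strongest reply is that this is a wording slip with the right answer already on paper. SAP section 2 brings in protocol section 9, SAP 2.3.1.4 gives the operative definition, and section 3 declares no switch. That largely stands. A reader might infer that the SAP has dropped the DAS28-CRP remission rates the protocol plans, or has deliberately moved to ESR. The documents do not support either inference: the planned rates are contradicted by 4.6.1.3, not removed from the plan.

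A second reply is that DAS28-ESR is a legitimate secondary measure. Protocol 6.4.1 says "whereas DAS28-ESR will only be used for secondary endpoint analysis", and protocol 9.5.2 lists it among the efficacy variables. Protocol Table 6-2 also gives a remission cut-off for DAS28 generically, which could be applied to the ESR score, so it would be wrong to say that no usable cut-off exists. This also stands, and it means an ESR table is permissible. It does not settle the conflict, because protocol 9.5.2 names DAS28-CRP specifically for the EULAR criteria, and SAP 4.6.1.3 neither calls the ESR version additional nor pairs it with a CRP table.

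Two neighbouring discrepancies carry little weight.

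- The SAP remission cut-off is below 2.6, while protocol Table 6-2 has 2.6 or below. The two differ only for a score of exactly 2.6. One might argue that rounding makes this common, since "for the DAS28-CRP and DAS28-ESR, 2 decimal places will be kept in the data listing", but that rule governs listings and nothing says that rounded scores are classified.
- SAP 4.2 describes patients eligible for Study Period 2 as "achieving at least a moderate EULAR response assessed by DAS28-CSR at Week 24". The index label is a clerical slip; SAP sections 1 and 2.3.1.4 already tie that criterion to DAS28-CRP.

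**Conclusion.** The conflict is real in the current text and should be corrected. SAP 4.6.1.3 assigns remission to DAS28-ESR, against the SAP's own definition and protocol 9.5.2, with no declared change. That follows from the wording alone and needs no assumption about the data.

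Its size is modest. The index can change an individual patient's remission status in either direction, as the two assumed patients show. The documents give no basis for saying how many patients would change, or whether either arm's rate would rise or fall. A reader might infer a bias in the comparison of GP2017 with Humira; that is not shown and is not claimed. The tables concerned are descriptive, with no margin or test attached. The primary analysis, the key secondary analysis and the sample size do not depend on them.

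**What to change.** In SAP 4.6.1.3, replace the reference to DAS28-ESR with a statement that EULAR good response, moderate response and remission are all derived from DAS28-CRP as defined in 2.3.1.4. If a DAS28-ESR version is wanted, present it as a labelled additional table with its own stated cut-off.

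In the same sentence, reconcile Week 36 with protocol 6.4.1: remove it, or say which assessments would supply a score then.

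Two small tidy-ups fit the same edit: align the remission cut-off between SAP 2.3.1.4 and protocol Table 6-2, and correct the index label in SAP 4.2 to DAS28-CRP.

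The cost is a few words in three SAP sections, plus confirmation of the input variable and visits for one set of descriptive tables. No new data are needed. The edit belongs before database lock, because SAP section 1 requires an addendum and an explanation in the study report for deviations after that point.

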4.6.1.4 Analysis of ACR over time

The number and proportion of patients achieving ACR20/50/70 at weeks 4, 12, 24, 36 and 48 will be summarized and plotted by treatment and visit.

The number and proportion of patient achieving EULAR/ACR Boolean remission criteria at weeks 4, 12, 24, 36 and 48, will be summarized and plotted by treatment and visit.

4.6.1.5 Analysis of HAQ-DI

The number and proportion of patients achieved HAQ-DI score with in normal range (≤ 0.5) at weeks 4, 12, 24, 36 and 48 will be summarized in a table by treatment group and visit.

HAQ-DI score at baseline and weeks 4, 12, 24, 36 and 48 will be summarized of descriptive statistics by treatment group and visit, which will be provided for both the absolute score, change and percent change from baseline, percent change from baseline will also be plotted.

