### Other secondary objectives

[figure not shown]
#### Study period 1: baseline (randomization) - Week 24

[figure not shown]
- To compare the proportion of GP2017 and US-licensed Humira® treated patients achieving EULAR criterion for remission at Week 4, 12, 24
- To compare the proportion of GP2017 and US-licensed Humira® treated patients achieving EULAR criterion for good response at Week 4, 12, 24
- To compare proportion of GP2017 and US-licensed Humira® treated patients achieved EULAR moderate response at Week 4, 12, 24
- To compare DAS28-CRP and DAS28-ESR changes from baseline in GP2017 and US-licensed Humira® treated patients at Week 2, 4, 24
- To compare the proportion of GP2017 and US-licensed Humira® treated patients achieving remission according to Boolean definition (TJC  $\leq 1$ , SJC  $\leq 1$ , CRP  $\leq 1$  mg/dl and patient global assessment (PtGA)  $\leq 1$ ) at Week 4, 12, 24
- To compare the proportion of GP2017 and US-licensed Humira® treated patients achieving ACR20/50/70 (based on CRP & ESR) responses at Week 4, 12, 24
- To compare Health Assessment Questionnaire-Disability Index (HAQ-DI) changes from baseline in GP2017 and US-licensed Humira® treated patients at Week 4, 12 and 24
- To compare the proportion of GP2017 and US-licensed Humira® treated patients achieving HAQ-DI score  $\leq 0.5$  at Week 4, 12 and 24
- To compare proportion of GP2017 and US-licensed Humira® treated patients with HAQ-DI score improvement  $> 0.3$  at Week 4, 12 and 24
- To compare FACIT Fatigue scale changes from baseline in GP2017 and US-licensed Humira® treated patients at Week 4, 12 and 24
- To compare CRP and ESR changes from baseline in GP2017 and US-licensed Humira® treated patients over time
- To compare clinical safety of GP2017 and US-licensed Humira® as assessed by changes in vital signs, clinical laboratory parameters and incidence and severity of Adverse Events (AE)
- To compare incidence and severity of injection site reactions (ISRs) in GP2017 and US-licensed Humira® treated patients

- To compare immunogenicity as determined by measuring the rate of anti-drug antibody (ADA) formation against adalimumab in GP2017 and US-licensed Humira® treated patients

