### **Premature patient withdrawal**

Patients may voluntarily withdraw from the study for any reason at any time. They may be considered withdrawn if they:

- State an intention to withdraw
- Fail to return for visits and after several attempts by the site personnel to reach this patients
- Become lost to follow up for any other reason

If such withdrawal occurs for any reason the investigator must determine the primary reason for a patient's premature withdrawal and record this information on the Study completion eCRF page. The investigator must also notify the IRT system of the premature withdrawal.

Patients who prematurely withdraw from the study, should be scheduled for a final assessment visit (as defined for EoS/ Visit 16), as described in [Table 6-1](#). For patients whose status is unclear because they fail to appear for study visits without stating an intention to withdraw, the investigator should show "due diligence" by contacting the patient, family or family physician as agreed in the informed consent and by documenting in the source documents steps taken to contact the patient, e.g. dates of telephone calls, registered letters, other.

If the investigator decides that a patient is not responding adequately to the study medication, patient should be withdrawn and may receive thereafter any anti-rheumatic treatments at the discretion of the investigator. Patient should undergo a final assessment visit which should be performed prior to treatment with the new anti-rheumatic therapy, and will then be withdrawn from the study. Lack of study drug efficacy should be stated on the study completion eCRF page for these patients.

Patients who are prematurely withdrawn from the study will not be replaced by newly enrolled patients.

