4.1 General considerations

4.1.1 Baseline definition

Unless stated otherwise, baseline is defined as the pre-dose assessment taken at Visit 2. For FACIT, HAQ-DI and Tender/swollen joints assessments baseline is defined on the questionnaire level, not on an individual measurements level.

For quantitative measurements, change and percent change from baseline will be calculated as:

- Change from baseline = Post-baseline value – Baseline value
- Percent change from baseline = $100\% * (\text{Post-baseline value} - \text{Baseline value}) / \text{Baseline value}$ for baseline values greater than 0.

Changes from baseline will only be summarized for patients having both baseline and post baseline values.

For the changes from Week 24 at Week 48 in terms of DAS28-CRP, DAS28-ESR, HAQ-DI score, and FACIT Fatigue scale, the nominal Week 24 and Week 48 visit values will be used.

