4.6.1.6 Analysis of FACIT

The absolute value, change and percent change from baseline for Functional Assessment of Chronic Illness Therapy (FACIT) Fatigue scale at weeks 4, 12, 24, 36 and 48 will be summarized as a continuous variable by treatment group and visit, percent change from baseline will also be plotted.

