4.7 Handing of missing data in the analysis

Refer to Section 2.3.1.1, [Appendix 1](#), and [Appendix 2](#).

5 Clinical Study Report – Appendix 16.1.9 Documentation of statistical methods

Appendix 16.1.9 of the CSR will contain the last SAP versions before database lock and the full SAS® outputs of the MMRM analyses of DAS28-CRP and DAS28-ESR as well as the ANCOVA analyses of the time-weighted averaged change from baseline approaches.

6 Appendices

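### HAQ-DI and FACIT-Fatigue changes are to be compared between products but get only observed-case tables, so response-driven withdrawal can distort the Week 24 comparison

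*SAP*

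**What the plan says.** **Objective.** Protocol 2.2 (Other secondary objectives, Study Period 1) includes: "To compare FACIT Fatigue scale changes from baseline in GP2017 and US-licensed Humira® treated patients at Week 4, 12 and 24". The HAQ-DI objective is worded the same way.

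**Analysis.** For HAQ-DI, SAP 4.6.1.5 states: "HAQ-DI score at baseline and weeks 4, 12, 24, 36 and 48 will be summarized of descriptive statistics by treatment group and visit". For FACIT, SAP 4.6.1.6 states that values and changes at "weeks 4, 12, 24, 36 and 48 will be summarized as a continuous variable by treatment group and visit". Neither section names a model, a treatment difference or an interval. This follows Protocol 9.5.2, which also has both scores only summarised.

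**Who is counted.** SAP 4.1.1: "Changes from baseline will only be summarized for patients having both baseline and post baseline values". The missing-data section, SAP 4.7, reads "Refer to Section 2.3.1.1" and adds the two date-imputation appendices. That covers joint counts and partial dates, not a missed questionnaire visit.

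**Contrast.** SAP 4.6.1.2 says the DAS28-CRP and DAS28-ESR changes at all visits "will be analyzed using the same MMRM method as for primary endpoint analysis". SAP 4.5 keeps any patient with at least one post-baseline change in that model.

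**Withdrawal.** Protocol 5.5.9: "If the investigator decides that a patient is not responding adequately to the study medication, patient should be withdrawn". Protocol 5.5.6 also takes users of RA rescue medication out of the study. Section 4 anticipates 20% post-randomization dropout.

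**The concern.** An observed-case mean at Week 24 describes patients who still have a Week 24 value. Here the protocol makes leaving partly a consequence of poor response, so the missing values are not a random sample. Two things follow. The Week 24 improvement in each arm looks larger than it would among all randomised patients. The between-arm difference, which is what the objective asks for, may be distorted, and the planned tables give no estimate or interval with which to judge it. Restricting to the SP1 PPS does not help, because SAP 2.7.2 limits that set to patients who complete Week 24. The FAS table has the same gap wherever the visit is absent. The SAP already contains a model that would use a withdrawn patient's Week 4 and Week 12 scores in estimating Week 24, but does not apply it to these two scores.

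**Working it through.** **1. The plan's own design figure.** The documents give a calculation for DAS28-CRP at Week 12 only (Protocol 9.6): SD 1.30, margin 0.6, true difference 0, 246 evaluable (123 per arm). Power = 2Φ(0.6/(1.30·√(2/123)) − z) − 1, and 0.6/(1.30·√(2/123)) = 3.62.
- 90% CI, z = 1.645: power 95.2%.
- 95% CI, z = 1.960: power 90.3%.
- 123/0.80 = 153.75, so 154 per arm.

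All stated figures reproduce. None concerns HAQ-DI or FACIT, and the point does not dispute them.

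**2. Illustrative simulation, common withdrawal rule.** Assumptions, none from the documents: 400,000 patients per arm; Weeks 4, 12 and 24; unit SD; visit correlation 0.5 or 0.7; true difference 0.46 SD at Weeks 12 and 24 (0.6/1.30, borrowed from DAS28-CRP) and 0.6 × 0.46 at Week 4. A patient leaves with probability 0.5 when the previous visit's change is worse than a threshold. The threshold is set for about 10% or 19% mean dropout, against the protocol's 20%. No End of Study value is mapped into Week 24.

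| Observed-case difference at Week 24 (SD) | Shrinkage, (0.46 − x)/0.46 |
|---|---|
| 0.411 | 10.7% |
| 0.403 | 12.4% |
| 0.396 | 13.9% |
| 0.389 | 15.4% |

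Repeat runs put the shrinkage at about 10–17%. A likelihood estimate using Weeks 4 and 12 returns 0.455–0.463. Each arm's improvement is overstated by 0.07–0.24 SD. With an assumed HAQ-DI SD of 0.6 that is 0.07 × 0.6 = 0.04 to 0.24 × 0.6 = 0.14 points.

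**3. Varying the assumptions.** Dropout is fixed at 20%, the share due to poor response varies over 25–100%, and the true difference is 0.2 or 0.46 SD.

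| Withdrawal driven by | Observed-case, % of truth | MMRM on FAS, % of truth |
|---|---|---|
| Last observed score | 76–93% | 97–101% |
| Unseen current score | 62–85% | 69–91% |

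With no true difference, both methods give about 0.

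**4. Different patterns by arm.** Suppose the better arm loses its worst 20% and the other loses 20% at random. The better arm's mean shifts by φ(0.842)/0.80 = 0.280/0.80 = 0.35 SD. A true 0.20 SD then appears as 0.20 + 0.35 = 0.55 SD, an overstatement.

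**5. Where the End of Study visit goes.** SAP 2.1.2 assigns it to a nominal visit only if it falls within that visit's window and the nominal visit is absent; otherwise it is tabulated separately. SAP 4.1.4 maps it to a scheduled visit by study day and states no window. Take a patient leaving at Week 16 (Day 113). Under 2.1.2 the value does not reach Week 24. Under 4.1.4, if the nearest of Weeks 12 and 24 is meant (an assumption), the midpoint is (85 + 169)/2 = Day 127, so again it does not, whereas a patient leaving at Day 141 would be counted.

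**The case against.** The strongest reply is that nothing is decided on these tables. No margin or hypothesis is attached to HAQ-DI or FACIT. Equivalence rests on DAS28-CRP at Week 12 and its time-weighted average, and Protocol 9.5.2 itself asks only for summaries. That stands, and it limits the weight of the point. It does not supply the between-product comparison named in Protocol 2.2.

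A reader might infer that withdrawn patients are simply discarded. The documents do not support that. Their Week 4 and Week 12 scores remain in those visits' tables. Week 24 non-responders are assessed at Week 24 before leaving (Protocol 5.2). A final visit with the Visit 16 assessments is scheduled for withdrawals (Protocol 6), and some of those values are mapped to scheduled visits. The proportion with HAQ-DI ≤0.5 uses the whole analysis set as denominator (SAP 2.1.2). What is lost is their contribution to later-visit means.

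A reader might also infer that the tables understate any product difference and so favour similarity. That needs a true difference and a common response-driven rule. Steps 3 and 4 show no bias without a difference, and overstatement under one unequal pattern.

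The size is assumption-driven too. The 20% is all-cause dropout and not tied to Week 24. In step 2 the between-arm bias is 0.46 − 0.411 = 0.05 to 0.46 − 0.389 = 0.07 SD, or 0.03–0.04 HAQ-DI points at SD 0.6. The standard error with 123 per arm is √(2/123) = 0.13 SD, so the bias is about half a standard error.

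Finally, the DAS28 contrast is partial: the primary MMRM runs on Week 12 completers (W12 PPS). Only the SP1 FAS run keeps patients who left before then.

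**Conclusion.** The point holds as a cheap improvement. The SAP gives observed-case description where the protocol promises a comparison, and the protocol's withdrawal rules make the Week 24 means unrepresentative of poor responders. Each arm's improvement is overstated. A true difference shrinks by roughly 10–17% in the illustrated common-rule case; over the wider grid with withdrawal driven by the last observed score the range is 7–24% (100% less 93% and 76%). It is not biased if the products are equal and share a withdrawal pattern, and the bias can reverse if patterns differ by arm. These sizes rest on assumed correlations, withdrawal mechanisms and a borrowed effect size, and they ignore mapped End of Study values. The primary and key secondary equivalence conclusions do not change.

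**What to change.** - In SAP 4.6.1.5 and 4.6.1.6, analyse change from baseline in HAQ-DI and FACIT-Fatigue at Weeks 4, 12 and 24 on the SP1 FAS with the Table 4-1 MMRM. Replace the DAS28-CRP baseline by the score's own baseline.
- Report the treatment difference with 95% CI at each of the three visits.
- Report missing counts by arm, visit and reason, so that a difference in withdrawal pattern can be seen.
- Keep the observed-case tables as description.
- Reconcile SAP 2.1.2 with 4.1.4 on when an End of Study value enters a scheduled visit.

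The cost is SAP wording and two more runs of an existing program, with no new data. The limit is that the estimates rest on missing at random. If withdrawal depends on scores not observed, the bias is reduced but not removed (69–91% of the truth recovered in step 3, against 62–85% for observed cases).
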